#### 6.14.4 Blood Cultures

Two sets of blood cultures via venipuncture will be obtained at Screening and sent to the local/regional laboratory. Repeat blood samples for culture should be taken as clinically indicated during the study. Blood cultures should be repeated after a positive result until

sterilization is documented. All organisms isolated from blood cultures which are not considered contaminants will be sent to the central laboratory for confirmatory identification and susceptibility testing. If possible, subjects who have confirmed *S. aureus* bacteremia should have blood samples collected for microbiologic culture prior to switch to alternate appropriate therapy. Culture results from the local/regional laboratory will be recorded in the eCRF.

#### 6.14.5 Serological Testing

Blood samples will be collected at Screening and LFU, and sent frozen to the central laboratory for serologic tests for *M. pneumoniae*, *C. pneumoniae* and *L. pneumophila*.

#### 6.14.6 Urine Antigen Test

A urine sample will be taken at Screening and tested at the clinical site for *L. pneumophila* and *S. pneumoniae* antigen testing. Results will be recorded in the eCRF. Subjects who have urinary antigen test positive for *Legionella sp.* at Screening will have a portion of the sputum sample collected at Screening sent to the central laboratory for *L. pneumophila* testing as described above (Section 6.14.1). Clinical sites that are unable to perform urinary antigen testing will send urine to the central laboratory for testing.

#### 6.14.7 Oropharyngeal Specimen

An oropharyngeal specimen (2 swabs) will be obtained at Screening and sent to the central laboratory/specialty laboratory for *M. pneumoniae* culture, susceptibility testing, as well as identification by PCR. Oropharyngeal specimens must be frozen until shipment to the central laboratory.

#### 6.14.8 Nasopharyngeal Specimen

A nasopharyngeal specimen will be obtained at Screening and sent to the central laboratory/specialty laboratory for *S. pneumoniae* culture, susceptibility testing, as well as identification by PCR. Nasopharyngeal specimens must be frozen until shipment to the central laboratory.

### 6.15 Health Utilization and Patient Reported Outcome

Exploratory evaluation of a variety of health utilization variables (e.g., length of hospital stay, duration of antibiotic therapy, discharge status, discharge destination) as well as a PRO instrument (SF-12) will be performed. Details for this exploratory analysis will be presented in a separate SAP and results will be presented in a stand-alone clinical study report.

### 6.16 Food and Beverage Restrictions

Subjects must comply with the following restrictions during their participation in the study:

- Subjects who are suspected to have MRSA as a pathogen and receive adjunctive (active or placebo) linezolid therapy should not be on a high tyramine diet. Large quantities of

foods or beverages with high tyramine content should be avoided while taking linezolid. Foods high in tyramine content include those that may have undergone protein changes by aging, fermentation, pickling, or smoking to improve flavor, such as aged cheeses, fermented or air-dried meats, sauerkraut, soy sauce, tap beers and red wines. The tyramine content of any protein-rich food may be increased if stored for long periods or improperly refrigerated. Further details regarding a high tyramine diet are provided in Appendix 6.

- Subjects should refrain from drinking alcohol throughout receipt of study drug.

In addition, as discussed in Section 5.6, doses of oral study drug should be administered at least 1 hour before a meal or 2 hours after a meal. However, in the event that a subject has taken any of the following – antacids containing aluminum, products containing iron, or multivitamins containing zinc – study drug should be administered 2 hours before or 4 hours after consuming any of these medications.

## 6.17 Discontinuation from Treatment or Study

Subjects are free to withdraw from the study at any time for any reason. Subjects may be withdrawn from study at the discretion of the Principal Investigator or Sub-Investigator at any time. Once a subject has been withdrawn from the study they may not be re-entered. Subjects who withdraw or who are withdrawn from the study will not be replaced. If a subject is discontinued from treatment or from the study, the reason for discontinuation will be collected in the eCRF.

### 6.17.1 Discontinuation from Treatment

A subject may be discontinued prematurely from study drug treatment for the following reasons:

- Lack of efficacy (i.e., requirement for additional non-study antibacterial therapy to treat the current episode of CABP)
- Adverse event
- Withdrawal by subject [specify reason in the eCRF]
- Lost to follow-up
- Physician decision (i.e., Investigator decision based on protocol violation, assessment that it is not in the subject's best interest to continue, or other reason) [specify reason in the eCRF]
- Sponsor decision [specify reason in the eCRF]

If a subject is prematurely withdrawn from study drug treatment, the Investigator should make every effort to retain the subject in the study and perform all procedures scheduled for the EOT, TOC and LFU visit. Any subject withdrawn from treatment due to an AE, SAE or clinically significant abnormal laboratory test value will be evaluated by the Investigator, or a

monitoring physician, and will be treated and/or followed up until the symptoms or values have either resolved or are assessed as stable by the Investigator.

#### 6.17.2 Discontinuation from Study

A subject may be discontinued prematurely from the study for the following reasons:

- Withdrawal by subject [specify reason in the eCRF]
- Lost to follow-up
- Death
- Physician decision (i.e., assessment that it is not in the subject's best interest to continue, or other reason) [specify reason in the eCRF]
- Sponsor decision [specify reason in the eCRF]

Every attempt will be made to contact subjects who withdraw from the study in order to determine their vital status (alive or dead) at Day 28.

#### 6.17.3 Individual Stopping Criteria

Subjects will be withdrawn from the study drug treatment for any of the following reasons:

- The subject demonstrates an average QTcF value > 500 ms (mean of 3 ECG's at any time point) as assessed locally by the Investigator. Such subjects should be observed until the ECG normalizes with repeat ECG's taken at the discretion of the investigator.
- The subject demonstrates an average QTcF value >480 ms with a concurrent increase in average QTcF value of > 60 ms (mean of 3 post-dose ECGs compared to mean pre-dose ECGs taken on that day) as assessed locally by the Investigator.
- The subject has confirmed *S. aureus* bacteremia.

If a subject is prematurely withdrawn from study treatment, the Investigator should make every effort to retain the subject in the study and to perform all procedures scheduled for the EOT, TOC and LFU visit. Any subject withdrawn from treatment due to an AE, SAE or clinically significant abnormal laboratory test value will be evaluated by the Investigator, or a monitoring physician, and will be treated and/or followed up until the symptoms or values have either resolved or are assessed as stable by the Investigator.

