- m: **At each required time point, ECGs should be recorded in triplicate within a 5-minute interval.** The subject should be stabilized in a supine position for 5 min before recording the ECG. Record ECGs at Screening. On Day 1 and Day 3 record ECGs prior to the first infusion of study drug on that day and within 15 minutes after the end of the first infusion on that day. If Screening and Day 1 are on the same day, the Screening ECG can serve as the Day 1 ECG prior to the first infusion of study drug. Additional ECG's may be performed if clinically indicated. If at any time the subject demonstrates an average QTcF value >500 ms (mean of 3 ECG's at any time point), or an average QTcF value >480ms with a concurrent increase in average QTcF value of > 60 ms (mean of 3 post-dose ECGs compared to mean pre-dose ECG's taken on that day) study drug will be discontinued.
- n: A complete physical examination is performed at baseline and directed physical examinations are performed on Day 4 (Day 3 is acceptable for outpatients who are not able to return on Day 4) and at EOT and TOC.
- o: For all subjects, collect blood and urine at Screening, Day 4 (Day 3 is acceptable for outpatients who are not able to return on Day 4), EOT, and TOC. In addition, for subjects receiving 10 days of study drug, collect blood and urine on Day 7 (Day 8 is acceptable for outpatients who are not able to return on Day 7). Subjects treated as outpatients must agree to return to the site for blood draws. Collect blood and/or urine at LFU only if subject had an abnormal (high/low flag) result at TOC. Blood samples sent to the local laboratory for the purposes of determining study eligibility must be repeated and sent to the central laboratory following enrollment.
- p: A pregnancy test will be performed on all females unless surgically sterile or at least 2 years post-menopausal. A negative urine pregnancy test is required prior to randomization and must be confirmed as soon as possible using a serum pregnancy test.
- q: Blood to be collected and sent to central laboratory for serologic tests for *M. pneumoniae*, *C. pneumoniae* and *L. pneumophila* at Screening and LFU.
- r: Record arterial blood gas and blood pH data if available. Study sites are not required to measure arterial blood gas or blood pH.

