## 1.5 Summary of Clinical Data

Lefamulin has been administered as single or multiple-doses orally and by IV infusions to healthy subjects in 17 completed Phase 1 studies and IV to subjects with ABSSSI in a completed Phase 2 study. In these studies, lefamulin was found to be safe and well tolerated at the doses to be used in the current study (150 mg IV over 60 minutes and 600 mg per oral administration).

In the 17 Phase 1 studies, 321 male and female healthy subjects were exposed to lefamulin, 12 of whom were  $\geq 65$  years of age. In the Phase 2 study, 141 subjects (95 male, 46 female) were exposed to lefamulin, 7 of whom were  $\geq 65$  years of age (4 in the 100 mg group, 3 in the 150 mg group) (Prince et al., 2010; Prince et al., 2013; Wicha et al., 2010; Zeitlinger et al., 2011).

Lefamulin PK is characterized by rapid absorption after oral administration. Steady-state is achieved after 2 days of q12h dosing, irrespective of the route of administration. After oral administration of an immediate-release tablet containing 600 mg of lefamulin, exposure — as measured by AUC (the driver of efficacy) — was similar to a 150 mg IV dose, the higher dose used in the Phase 2 study in ABSSSI (NAB-BC-3781-2001) (Wicha et al., 2013).

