The effect of lefamulin on the cardiac conduction parameters of RR, QT, and QTcF has been closely monitored in all clinical studies. A  $C_{max}$ -dependent, predictable, and reproducible prolongation of the QT/QTcF interval has been observed. A thorough analysis of ECGs in the Phase 2 study demonstrated that lefamulin prolonged cardiac depolarization and repolarization duration, but otherwise had a similar cardiac safety profile to that of vancomycin based on evaluations of 12-lead ECGs. Therefore, it is expected that lefamulin will not produce large effects on cardiac de- and repolarization duration. No drug-related cardiac AE — such as increase in ectopic ventricular activity or other cardiac arrhythmia — or clinically relevant ECG findings was reported during the conduct of the studies. None of the protocol-defined stopping criteria (i.e.,  $QTcF > 500$  ms and  $\Delta QTcF > 60$  ms) was reached in any clinical study.

In summary, the results of the Phase 2 study provide the first proof of concept for the systemic use of a pleuromutilin antibiotic in subjects and support the further clinical evaluation of lefamulin for therapy of serious infections. Pharmacokinetic/pharmacodynamics analyses suggest that lefamulin 150 mg IV q12h is an efficacious dosing regimen for Phase 3 studies. Based on available safety data, lefamulin 150 mg IV q12h produced therapeutic exposures and demonstrated an acceptable benefit/risk profile for the treatment of infected subjects. Oral doses of 600 mg lefamulin produced similar systemic exposures to 150 mg IV with a similar benefit/risk profile and were well tolerated with no signs or symptoms of clinical concern.

This is the first Phase 3 study to be conducted in subjects with a systemically-administered pleuromutilin antibiotic. The population in this study will be subjects with CABP and they

will receive treatment with either lefamulin or moxifloxacin (with or without adjunctive linezolid), a standard treatment for this condition.

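### The QTcF stopping limb for a rise above 60 ms uses only same-day pre-dose ECGs, so on Day 3 a larger rise from the drug-free value need not stop study drug

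*Protocol*

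**What the plan says.** Section 6.17.3 lists three reasons for mandatory withdrawal from study drug. Two are QTcF limbs: a triplicate mean above 500 ms at any time point, and a mean above 480 ms together with a rise of more than 60 ms. For the second limb the rise is defined as "mean of 3 post-dose ECGs compared to mean pre-dose ECGs taken on that day". Footnote m to Table 3 repeats the rule with the same reference ("mean of 3 post-dose ECGs compared to mean pre-dose ECG's taken on that day") and applies it whenever the values are seen.

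The same footnote sets the ECG schedule. After Screening, the instruction is "On Day 1 and Day 3 record ECGs prior to the first infusion of study drug on that day" and again "within 15 minutes after the end of the first infusion on that day". If Screening and Day 1 coincide, "the Screening ECG can serve as the Day 1 ECG prior to the first infusion of study drug". Beyond that, "Additional ECG's may be performed if clinically indicated", with no requirement that such an ECG be paired with a pre-dose tracing.

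On the drug itself, Section 1.5 states "Steady-state is achieved after 2 days of q12h dosing, irrespective of the route of administration", and Section 1.5.3 says that a Cmax-dependent, "predictable, and reproducible prolongation of the QT/QTcF interval has been observed".

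**The concern.** The purpose of a limb of this kind is to catch a large individual rise before QTcF reaches 500 ms. Its reference should therefore include a drug-free value. On Day 1 the pre-infusion ECG is drug-free and the limb works. On Day 3 the pre-infusion ECG is taken on treatment, so part of the drug's effect may already sit in the reference and drop out of the difference. For an unscheduled ECG on any other day there may be no same-day pre-dose ECG, and the limb then cannot be evaluated.

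The protocol elsewhere treats the change in QTcF as change from baseline. The abbreviation list defines ΔQTcF that way, Section 1.5.3 states the earlier studies' stopping criteria in terms of ΔQTcF, and Section 9.7 analyses change from baseline. Only the stopping rule uses a different reference, and no reason is given. At stake is a mandatory safety floor for a drug with an acknowledged QT effect. Where the limb fails to fire, stopping becomes a matter of investigator discretion.

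**Working it through.** The protocol gives no figure to reproduce here and no subject-level QTcF, so the check is of the rule itself. All millisecond values below are illustrations.

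**Inputs**
- Second limb: mean above 480 ms and rise above 60 ms, same-day reference (Section 6.17.3; Table 3 footnote m).
- First limb: mean above 500 ms, no reference needed. The second limb therefore matters only above 480 and up to 500 ms.
- Scheduled on-treatment ECGs: Days 1 and 3 only (footnote m).
- Doses before the Day 3 morning infusion: normally 2 + 2 = 4 at q12h, or 1 + 2 = 3 if only one was given on Day 1 (Section 5.6). Lefamulin is at about steady state after 2 days (Section 1.5).

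**Notation.** D is the drug-free mean, S the same-day pre-dose mean and P the post-dose mean, with 480 < P ≤ 500. The current rule stops if P − S > 60. A rule accepting either reference stops if P − D > 60 or P − S > 60.

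| D / S / P (ms) | P − D | P − S | Current rule | Either reference |
|---|---|---|---|---|
| 425 / 440 / 490 | 65 | 50 | no stop | stop |
| 420 / 430 / 485 | 65 | 55 | no stop | stop |
| 415 / 440 / 500 | 85 | 60 | no stop | stop |
| 400 / 440 / 499 | 99 | 59 | no stop | stop |
| 425 / 425 / 490 | 65 | 65 | stop | stop |
| 440 / 425 / 490 | 50 | 65 | stop | stop |
| 425 / none / 490 | 65 | – | not evaluable | stop |

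**Where the Day 3 gap lies.** It needs D < P − 60 and S ≥ P − 60. The cut-point P − 60 is 421 ms at P = 481, 430 ms at P = 490 and 440 ms at P = 500.

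**How much pre-dose shift opens it.** Let R = P − D. Then P − S = R − (S − D), so the current rule does not stop once S − D ≥ R − 60. For R = 65, 70 and 80 ms the shift needed is 5, 10 and 20 ms. This step uses no pharmacokinetic assumption.

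**If a fraction f of the total rise is already present pre-dose** (an assumption; the protocol does not give f), the limb fires only when R(1 − f) > 60, that is R > 60/(1 − f):
- f = 0.05: 63 ms
- f = 0.10: 67 ms
- f = 0.20: 75 ms
- f = 0.30: 86 ms

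Taking the half-life range in Section 1.5.1 (8.6 to 11.8 h) over 12 h gives f of about 0.38 to 0.49 and thresholds of about 97 to 118 ms. That is an upper bound, because it ignores the rapid distribution phase described in the same section.

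**Does adding the second reference lose any stop?** No. The current condition is one of the two alternatives, so it can only add stops. A check over D and S from 380 to 480 ms and P from 481 to 500 ms in whole milliseconds found 0 cases that stop now but not under the either-reference rule. Replacing the same-day reference outright would lose stops, as the 440 / 425 / 490 row shows.

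**Days without a scheduled ECG.** 7 − 2 = 5 of 7 dosing days, or 10 − 2 = 8 of 10. On those days the limb can be applied only if a same-day pre-dose ECG happens to have been taken.

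**The case against.** The rule is stated identically in both places, so it is a design choice and not a contradiction. A same-day reference can be defended: the effect is Cmax-dependent, and a pre-infusion and post-infusion pair isolates the acute effect of that infusion. The drug-free ECG is taken in acute illness, since entry requires at least two abnormal vital signs, so a change from Screening to Day 3 mixes drug effect with recovery. The protocol does not give this rationale, but it is reasonable. It supports keeping the same-day reference; it does not support having no other.

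The event is probably rare. Section 1.5.3 says no earlier study reached its stopping criteria, and Section 1.5 counts 321 + 141 = 462 subjects exposed to lefamulin. If the ΔQTcF criterion there meant any rise above 60 ms from a drug-free value, the rule-of-three upper bound is 3/462, about 0.65%. Those subjects were healthy or had skin infections, and doses varied, so the figure transfers only loosely to pneumonia. The rapid distribution phase also points to a small trough effect. The steady-state statement covers lefamulin only; the protocol gives no corresponding information for moxifloxacin. All of this limits the size of the gap but does not close it.

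Other safeguards exist. The investigator or designee reviews all ECGs (Section 6.3), drug may be stopped for an adverse event or by physician decision (Section 6.17.1), the limb above 500 ms is intact, and Section 9.7 includes change-from-baseline and outlier analyses. The rise would therefore not go unseen. But the first two safeguards are discretionary, the third applies only above 500 ms, and the analyses stop no individual subject.

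Finally, extra stops carry an efficacy cost. A Day 3 stop falls before the window for Early Clinical Response opens at 72 hours. A subject who then receives another antibiotic for the pneumonia counts as a non-responder on that endpoint and as a Failure on the Investigator's Assessment of Clinical Response. That is true, and it belongs in the cost of the change. The number of subjects should be small.

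**Conclusion.** The concern holds, as a cheap improvement to patient safety. As written, the second limb may not require a stop on Day 3 for a subject more than 60 ms above the drug-free value, and it may not be evaluable for an unscheduled ECG on a day without a pre-dose tracing. The gap is limited to post-dose means above 480 and up to 500 ms. Its frequency cannot be estimated from the protocol and is probably low.

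The conclusion rests on the wording of the rule and on the Day 3 pre-dose ECG being an on-drug measurement. It does not rest on any assumed size of carry-over, although the number of subjects affected would depend on that. No effect on the primary comparison is claimed.

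**What to change.** In Section 6.17.3 and in footnote m to Table 3, require study drug to stop if mean QTcF is above 480 ms and the rise exceeds 60 ms from either (a) the mean of the drug-free ECGs taken at Screening or before the first infusion on Day 1, or (b) the mean of the same-day pre-dose ECGs where these were taken. State that this applies to scheduled and unscheduled ECGs alike. Leave the limb above 500 ms unchanged, and do not drop the same-day reference.

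The cost is amendment wording in two places. No additional ECG is needed, because a drug-free tracing is already required before the first dose, and every stop required today is still required. The downside is possibly a few more treatment discontinuations, some of which would count as efficacy failures if non-study antibiotics follow.

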#### 6.17.4 Lost to Follow-up

Every reasonable attempt should be made to retain subjects in the study. If a subject does not report to the study site for a scheduled visit, study personnel will make 4 contact attempts: 3 telephone contact attempts and, if these are unsuccessful, a certified letter will be sent to the subject. The subject will be considered lost to follow-up if (1) upon receipt of delivery confirmation of the certified letter the subject does not contact the site or (2) the certified letter is returned as undeliverable. Every attempt will be made to contact subjects who withdraw from the study in order to determine their status (alive or dead) at Day 28.

## 7 ADVERSE EVENTS

An adverse event (AE) is any untoward medical occurrence in a subject or clinical investigation subject administered a pharmaceutical product that does not necessarily have a causal relationship with this treatment. An AE can therefore be any unfavorable and unintended sign (including an abnormal laboratory finding), symptom, or disease temporally associated with the use of an investigational product, whether or not related to the investigational medicinal product.

Any pre-existing conditions or signs and/or symptoms present in a subject prior to the start of the study (i.e., before informed consent) should be recorded as medical/surgical history. Any medical occurrences which are new or worsened from the time of informed consent and up to and including the final visit must be reported as AEs or SAEs. All AEs and SAEs must be recorded irrespective of whether they are considered drug related. NOTE: lack of efficacy/clinical failure does not have to be recorded as an AE unless it is an SAE.

Subjects will be monitored throughout the study for adverse reactions to the study medications and/or procedures at each study visit. Questions will be posed in a non-leading manner so as not to bias the response. In addition to questioning at specific time points, subjects will be encouraged to spontaneously report any AEs. Any subject with an AE, SAE or clinically significant abnormal laboratory test value will be evaluated by the Investigator, or a monitoring physician, and will be treated and/or followed up until the symptoms or values have resolved or are assessed as stable by the by the Investigator. A physician, either at the Investigative site or at a nearby hospital emergency room, will administer treatment of any SAEs. Where appropriate, medical tests and examinations may be performed to ensure that an AE has fully resolved.

Adverse events will be monitored throughout the study from the time a subject is consented through the TOC visit; SAEs are to be collected from the time of consent through the LFU visit. Whenever possible, a specific disease or syndrome rather than individual associated signs and symptoms should be identified by the Investigator and recorded on the subject's eCRF. However, if an observed or reported sign or symptom is not considered a component of a specific disease or syndrome by the Investigator, it should be recorded as a separate AE on the subject's eCRF.

Each AE or SAE reported will be assessed for intensity and the date and time of onset (if available), time relationship to dosing, duration, and outcome of each event will be noted.

Laboratory abnormalities are not considered AEs unless they are associated with clinical signs and symptoms or require medical intervention. Clinically significant abnormal clinical laboratory findings or other abnormal assessments that are associated with the disease being studied, unless judged by the Investigator as more severe than expected for the subject's condition, or that are present or detected at the start of the study and do not worsen, will not be reported as AEs or SAEs.

The Investigator will exercise medical and scientific judgment in deciding whether an abnormal clinical laboratory finding or other abnormal assessment is clinically significant.

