All SAEs for subjects occurring from the time of informed consent through the LFU visit must be reported to Nabriva Therapeutics AG or their representative within 24 hours of the knowledge of the occurrence (this refers to any AE that meets one or more of the aforementioned serious criteria). Reporting is done by completing the SAE form electronically in the Electronic Data Capture (EDC) system for the study. When the form is completed, PPD Pharmacovigilance (PVG) will be notified electronically and will retrieve the form. If the event meets serious criteria and it is not possible to access the system, site must fax the completed paper SAE report form to PPD PVG within 24 hours of awareness or call the PPD PVG SAE hotline. When the EDC system becomes available, the SAE information must be entered within 24 hours of the system becoming available. PPD PVG personnel are available for SAE reporting on a 24 hour basis. Reports are reviewed during normal business hours. EDC and/or report forms should be completed in as much detail as possible but lack of complete information should not delay the reporting of the SAE.

There may be situations when an SAE has occurred and the Investigator has minimal information to include in the initial report to Nabriva Therapeutics AG, or their representative. However, it is very important that the Investigator always makes an assessment of causality for every event prior to transmission of the SAE report form to Nabriva Therapeutics AG, or their representative. The Investigator may change his/her opinion of causality in light of follow-up information, amending the SAE report form accordingly. The causality assessment is one of the criteria used when determining regulatory reporting requirements.

The Investigator will provide the assessment of causality as per instructions on the SAE form in the subject's eCRF. SAEs that are determined by the Investigator to be related to the study drug must be reported even if more than 30 days after the last administration of study drug.

The sponsor will not routinely unblind the therapy assignment for an individual subject in the event of a serious adverse event. However, unblinding of an individual subject may occur if this information is requested by the Investigator, if the Sponsor determines that the information is necessary to adequately assess safety, or if this information is required for reporting to local regulatory authorities (see Section 5.9).

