## **7.4 Symptoms of the Disease Under Study**

In this study, clinical signs and symptoms of pneumonia which are assessed daily per protocol (i.e., dyspnea, cough, sputum production, and chest pain) will not be reported as adverse events unless they meet the definition of a serious adverse event.

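### Section 7 bars disease-associated abnormal findings judged no worse than expected from SAE reporting, with no exception for seriousness, and so conflicts with Section 7.3

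*Protocol*

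**What the plan says.** The last part of the general text of Protocol Section 7 contains one sentence with two limbs and a shared ending.

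- **Disease-associated limb.** It covers "Clinically significant abnormal clinical laboratory findings or other abnormal assessments that are associated with the disease being studied" and is lifted only "unless judged by the Investigator as more severe than expected for the subject's condition".
- **Baseline limb, with the shared ending.** "or that are present or detected at the start of the study and do not worsen, will not be reported as AEs or SAEs".

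Just before it, the section limits when a laboratory value is an AE at all: "Laboratory abnormalities are not considered AEs unless they are associated with clinical signs and symptoms or require medical intervention".

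The neighbouring rules are these:

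- Earlier in Section 7, any occurrence that is new or has worsened since consent must be reported as an AE or SAE, whether or not it is thought drug-related.
- Also in Section 7, "lack of efficacy/clinical failure does not have to be recorded as an AE unless it is an SAE".
- Section 7.3 defines an SAE by its outcome, such as death, threat to life, or prolonged hospitalization. It exempts nothing as disease-related or expected, and adds: "All SAEs for subjects occurring from the time of informed consent through the LFU visit must be reported".
- Section 7.4 says that dyspnea, cough, sputum production and chest pain "will not be reported as adverse events unless they meet the definition of a serious adverse event".
- Section 7.5 makes any Potential Hy's Law case promptly reportable, and reportable as an SAE if the investigator finds it serious.

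**The concern.** The words on SAEs in the shared ending carry no exception for seriousness. In the disease-associated limb, the only way back into reporting is the investigator's view that the finding is worse than expected for that subject. Expectedness and seriousness are different questions: an abnormality can be just what one expects in PORT class III to V pneumonia and still prolong a hospital stay. A site following this sentence would withhold such an event, while a site following Section 7.3 would report it within 24 hours.

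The sentence also puts attribution to the disease ahead of reporting. Section 7.2 already asks the investigator to weigh the natural history of the underlying disease when judging causality. An event excluded beforehand never gets that assessment and does not reach expedited reporting. With about 125 centers, two incompatible instructions on a mandatory duty invite differences in practice between sites.

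**Working it through.** No figure in the protocol bears on this point, so the check is a comparison of rules.

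| Rule | What it covers | Does seriousness restore reporting? |
|---|---|---|
| Section 7, disease-associated limb | Abnormal laboratory findings and other assessments linked to the pneumonia | No; only a judgement of worse than expected does |
| Section 7, baseline limb | Findings present at the start that do not worsen | No |
| Section 7, lack of efficacy | Clinical failure | Yes |
| Section 7.4 | Four daily-assessed symptoms | Yes |
| Section 7.5 | Potential Hy's Law | Always reportable; an SAE if serious |
| Section 7.3 | Every SAE from consent to late follow-up | Reporting is unconditional |

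**Step 1: which limb matters.** The baseline limb applies only while a finding does not worsen, so it cannot concern deterioration. The condition about not worsening belongs to that limb alone. A disease-associated finding that is new or worsens on study stays excluded if it is thought expected.

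**Step 2: a test case.** Suppose oxygen saturation falls on study, the fall is attributed to the pneumonia, it is judged no worse than expected, and it prolongs the hospital stay.

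- Disease-associated limb: not reported, as AE or SAE.
- Section 7 general rule: reported, because it has worsened since consent.
- Section 7.3: reported, because prolonged hospitalization is a serious criterion.

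The instructions cannot all be followed.

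**Step 3: does the laboratory rule remove the conflict?** No. For laboratory values, that rule admits an abnormality as an AE if it comes with symptoms or needs intervention, which a serious one usually would. The next sentence then excludes it again if it is disease-associated and thought expected.

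**Step 4: how much is left.** Several other routes would capture the same patient:

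- the general duty to report new or worsened occurrences, with Section 7's preference for recording the disease or syndrome over its component signs;
- serious symptoms under Section 7.4 (Table 8 grades dyspnea requiring oxygen therapy as severe);
- clinical failure that is an SAE;
- Potential Hy's Law under Section 7.5.

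What remains is an abnormal finding that is disease-associated, judged no worse than expected, itself the thing that meets a serious criterion, and not recorded by any of these routes.

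**The case against.** The strongest reply is that this is a drafting wrinkle. The sentence is about findings, whereas an SAE is an occurrence with a serious outcome. A deterioration that prolongs hospitalization will normally be recorded as a clinical event, a serious symptom or a serious failure, and the exclusion lifts once the finding is worse than expected. Safety data also arrive by other channels. Scheduled laboratory tests go to a central laboratory (Section 6.12), oxygen saturation and supplemental oxygen are recorded (Section 6.4), laboratory and vital-sign changes are summarized by arm (Section 9.7), and the DMC sees summary safety data by masked arm (Sections 5.8 and 10.2).

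Most of this stands, and it rules out four stronger readings that a reader might infer:

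- **That Section 7 contradicts Section 7.4.** Section 7.4 governs four symptoms; the disputed sentence governs laboratory findings and other assessments. They differ in approach but do not collide.
- **That serious deterioration in general escapes SAE reporting.** The routes above keep most of it reportable.
- **That drug harm to liver or kidney is filtered out.** Nothing in the protocol calls rising transaminases a pneumonia finding, Potential Hy's Law cases are reportable regardless, and laboratory data are analyzed whether or not an AE is recorded.
- **That a number of missed SAEs can be given.** The protocol states no SAE rate, no share resting on such findings and no share judged expected.

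The reply does not remove the literal conflict with Section 7.3. The other routes work only if the site uses them, and the sentence tells the site not to report the finding as an SAE.

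**Conclusion.** Wrong as written, but minor. The disease-associated limb gives a reporting instruction that conflicts with Section 7.3 and with Section 7's general rule on new or worsened occurrences. It also departs from the seriousness exception used for clinical failure and for pneumonia symptoms, which suggests a drafting slip and not a policy. The conclusion rests on the text alone, reading the shared ending as applying to both limbs, which the grammar of the sentence requires.

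The gap is the residual case in Step 4. Its frequency cannot be derived from the protocol. Sample size, power and the efficacy analyses are unaffected.

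**What to change.** Reconcile the Section 7 sentence with Section 7.3. Split it into its two limbs and add to the disease-associated limb only: *unless they meet a serious criterion in Section 7.3, in which case they are reported as SAEs*. Keep the existing clause on findings worse than expected, and leave the limb on baseline findings that do not worsen unchanged.

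The restriction to one limb matters. SAEs are collected from consent, hospitalization is a serious criterion, and subjects need not be in hospital at entry (Section 5.6). If the exception also reached the baseline limb, unchanged hypoxemia that helped qualify a subject could become an SAE merely because the subject was admitted after consent.

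The cost is one sentence in the next amendment, a line in site safety training, and slightly more SAE reports.
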